### **4.6.2 Study Treatment Discontinuation**

Patients must discontinue study treatment (and will continue in the study) if they experience any of the following:

- Requirement of any prohibited medication as defined in [Section 4.4.2](#)
- Treated with accepted immunosuppressive that exceeds the maximum dose as defined by the protocol (see [Section 4.4.1](#))
- Combination immunosuppressive medications not allowed in the inclusion and exclusion criteria (see [Section 4.1](#))

- Grade >2 AST or ALT elevation: (AST or ALT >3×ULN) in combination with total bilirubin >2×ULN or clinical jaundice as defined by Hy's law
- Grade ≥3 AST or ALT elevation: (AST or ALT >5×ULN)
- Grade 4 Neutropenia: ANC <500/mm^3
- Grade 4 Lymphopenia: absolute lymphocyte count (ALC) <200/mm^3
- Grade 4 Thrombocytopenia: platelet count <25,000/mm^3
- Pregnancy
- Malignancy (with the exception of non-serious local and resectable basal or squamous cell carcinoma of the skin)
- An episode of torsade de pointes

Patients must discontinue study treatment if they receive any new or increased dose of SLE treatment that is not specifically permitted in this protocol (see Section 4.4.1) and approved by the Medical Monitor.

Investigators may discontinue study treatment for:

- Any medical condition that may jeopardize the patient's safety if he or she continues on study treatment
- The best interest of the patient
- Patient non-compliance

If study treatment is discontinued prematurely, patients will be asked to stay in the study and continue with all scheduled visits for the remainder of the 48-week treatment period.

The primary reason for study treatment discontinuation should be documented on the appropriate eCRF. Patients who discontinue study treatment prematurely will not be replaced.

In some cases, study treatment may be resumed if approved by both the investigator and the Medical Monitor.

#### **4.6.3 Study and Site Discontinuation**

The Sponsor has the right to terminate this study at any time. Reasons for terminating the study may include, but are not limited to, the following:

- The incidence or severity of adverse events in this or other studies indicates a potential health hazard to patients.
- Patient enrollment is unsatisfactory.

The Sponsor will notify the investigator if the Sponsor decides to discontinue the study.

The Sponsor has the right to close a site at any time. Reasons for closing a site may include, but are not limited to, the following:

- Excessively slow recruitment
- Poor protocol adherence
- Inaccurate or incomplete data recording
- Non-compliance with the International Conference on Harmonisation (ICH) guideline for Good Clinical Practice
- No study activity (i.e., all patients have completed the study and all obligations have been fulfilled)

## **5. ASSESSMENT OF SAFETY**

### **5.1 SAFETY PLAN**

To protect patient safety, an unblinded IMC in collaboration with a Scientific Oversight Committee will monitor safety throughout the study (see Section [3.1.2](#)).

The safety risk management plan for patients in this study is based on nonclinical and clinical experience with GDC-0853 in completed and ongoing studies as well as published literature on other BTK inhibitors and takes into account the population under study. The important potential safety risks for GDC-0853 are outlined below. Please refer to the GDC-0853 Investigator's Brochure for a complete summary of safety information.

Several measures will be taken to ensure the safety of patients participating in this study. Eligibility criteria have been designed to exclude patients at higher risk for potential toxicities. Patients will undergo safety monitoring during the study, including monitoring of vital signs, physical examination, ECGs, and routine laboratory safety assessments (hematology, chemistry, and urinalysis) and assessment of the nature, frequency, and severity of adverse events. In addition, guidelines for managing potential adverse events, including criteria for treatment interruption or discontinuation, and enhanced safety reporting are provided below and in [Table 5](#).

#### **5.1.1 Safety Plan for Potential Risks Associated with GDC-0853**

##### **5.1.1.1 Infections**

On the basis of the well described phenotype of patients with XLA, a primary immunodeficiency of B cells and immunoglobulin production, it is anticipated that inhibitors of BTK may raise the risk for certain bacterial infections ([Lederman and Winkelstein 1985](#); [Broides et al. 2006](#)), enteroviral infections ([Misbah et al. 1992](#); [Ziegner et al. 2002](#)), intestinal infections with *Giardia* and *Campylobacter species* ([Winkelstein et al. 2006](#); [van den Bruele et al. 2010](#)), or other opportunistic infections which are primarily cleared by B-cell adaptive immune responses. This risk is likely independent of sex for patients exogenously administered GDC-0853.

Unlike XLA, GDC-0853 is a reversible inhibitor of BTK that will be initiated after the immune system has developed, and so the degree to which GDC-0853 antagonism of BTK signaling may suppress immune activity or resemble XLA is unknown. However, data to date suggest that since BTK inhibitors target only the kinase domain, other BTK activities may remain intact and IgG levels in patients with an established immune system may not be significantly depleted (Byrd et al. 2013).

Effects on lymphocytes and immunoglobulins in rats and dogs were reversible and considered to be related to pharmacological activity involving BTK inhibition. See Section 1.3.1 for related primary nonclinical toxicity findings and Section 4 of the GDC-0853 Investigator's Brochure for further details.

To date, no immune-challenge experiments (e.g., T-dependent antigen response test [TDAR]) have been conducted in animals. It is not known if these effects on B cells and IgG concentrations in animals will translate to humans, or if such changes would have functional/deleterious impact on immune function.

Infections, including pneumonia and fatal influenza, have occurred in patients with B-cell malignancies treated with GDC-0853. In studies with healthy subjects with single doses and with dosing for 14 days, self-limited Grade 1 events of nasopharyngitis were reported but did not lead to any change in study drug dosing. One subject had asymptomatic bacteriuria, which resolved while study drug dosing continued.

Patients will be excluded from the study if they have a history of any major episode of infection requiring hospitalization or treatment with IV or IM antimicrobials within 4 weeks prior to or during screening or treatment with oral antimicrobials within 2 weeks prior to and during screening, evidence of active or latent or inadequately treated infection with TB, known active infection (current) or history of recurrent infection, or any known immunodeficiency including IgG < 500 mg/dL (see Section 4.1.2).

Total Ig concentrations will be measured regularly throughout the study. All patients in the study should be monitored for fever and potential infectious complications, including opportunistic infections and tuberculosis, and should be evaluated promptly. Physicians or a health care provider should give patients advice to prevent potential transmission of and exposure to endemic infections according to local or CDC guidelines. Patients should be advised to seek immediate medical attention if they develop signs and symptoms suggestive of an infection. All infections occurring during the study that require treatment, including, but not limited to, respiratory infections, cutaneous infections, urinary tract infections and systemic viral infections and episodes of suspicious or febrile diarrhea, should be evaluated using serology or PCR (if available, *and as appropriate*) and cultured if feasible and any identified organisms noted in the Adverse Event eCRF. Any serious infection, any infection requiring IV antimicrobials (i.e., any Grade 3 infection), or any opportunistic infection is considered an adverse

event of special interest (AESI) and should be reported to the Sponsor in an expedited manner as outlined in Section 5.2.3.

Guidelines for management of study treatment in the event that a patient experiences an infection are provided in Table 4.

#### **5.1.1.2 Vaccinations**

The effect of GDC-0853 upon the efficacy of vaccinations is unknown. It is recommended that appropriate vaccinations per EULAR (van Assen et al. 2011) recommendations or local guidelines be up to date before study participation. Patients will be excluded from study participation and will not be dosed with GDC-0853 if they have been vaccinated with live, attenuated vaccines (e.g., the intranasal live attenuated influenza vaccines, BCG, varicella) within 6 weeks before planned dosing. Immunization with a live or attenuated vaccine is prohibited for the duration of study participation, including the safety follow-up period after the administration of the last dose however inactivated vaccine formulations are permitted (e.g., seasonal influenza).

In addition, current routine household contact with children or others who have been vaccinated with live vaccine components may pose an unknown risk to the patient during study treatment with GDC-0853. Some of these vaccines include varicella (“chickenpox”) vaccine, oral polio vaccine, and the inhaled flu vaccine. Following vaccination with live component vaccines, the virus may be shed in bodily fluids, including stool, and there is a potential risk that the virus may be transmitted to the patient.

General guidelines for immunosuppressed patients suggest that exposure to vaccinated individuals should be avoided following vaccination with these vaccines for the stated time periods:

- Varicella or attenuated typhoid fever vaccination for 4 weeks following vaccination;
- Oral polio vaccination for 6 weeks following vaccination;
- Attenuated rotavirus vaccine for 10 days following vaccination;
- FluMist® (inhaled flu vaccine) for 1 week following vaccination.

#### **5.1.1.3 Bleeding**

No decrease in platelets, changes in coagulation parameters or bleeding events were observed in nonclinical studies with GDC-0853. Bleeding events, including non-serious CTCAE Grade 1 bruising and serious Grade  $\geq 3$  GI bleeding have been reported in patients with hematological malignancies treated with GDC-0853 in Study GO29089. The GI bleeding events have not been dose related, and the events occurred in patients who were taking concomitant NSAIDs/acetylsalicylic acid and who had a history of gastroesophageal or peptic ulcer disease. The impact of BTK inhibition as a potential risk factor for bleeding is unknown. BTK is expressed in platelets and is involved in platelet function via GPVI/Collagen receptor signaling and GP1b receptor signaling. Platelets from patients with XLA, a genetic deficiency of BTK, demonstrate decreased

activation in response to submaximal collagen stimulation but normal response to thrombin; clinically, there is no reported bleeding propensity of XLA patients ([Howard et al. 2006](#)).

Bruising or bleeding events related to GDC-0853 have not been reported in healthy subjects.

It is unknown if GDC-0853 will increase the risk of bleeding in patients, especially in those receiving antiplatelet or anticoagulant therapies. As a precautionary safety measure, patients will be excluded from study participation if they have a need for systemic anticoagulation with warfarin or other oral or injectable anti-coagulants or anti-platelet agents (other than NSAIDs, aspirin, and other salicylates), any history of hospitalizations or transfusion for a GI bleed, any history of a hemorrhagic CVA, any history of spontaneous intracranial hemorrhage, traumatic intracranial hemorrhage within 10 years prior to the study or a known bleeding diathesis. Patients should be advised to seek immediate medical attention if they develop signs and symptoms suggestive of clinically significant bleeding.

Several risk factors including patient age, co-morbidities, concurrent medications, prior medical history, and *Helicobacter pylori* infection have been demonstrated in a variety of studies to increase the risk of NSAID-related GI injury ([Lanza et al. 2009](#)). It is unknown if GDC-0853 will increase the risk of bleeding in patients receiving NSAIDs. Therefore, in order to prevent NSAID-related GI complications in high-risk patients, concomitant use of PPI should be considered ([Bhatt et al. 2008](#)) and used according to local or recognized guidelines (e.g., ACCF/ACG/AHA 2008 Expert Consensus Document).

Patients at high risk for NSAID-related GI toxicity include the following:

- Patients using both aspirin and an NSAID
- Patients with a history of ulcer disease
- Patients with one or more of the following:
  - Age  $\geq$  60 years
  - High-dose NSAID use
  - Concurrent corticosteroid use
  - Dyspepsia or gastroesophageal reflux disease (GERD) symptoms

Any bleeding event Grade  $\geq$  2 is considered an adverse event of special interest and should be reported to the Sponsor in an expedited manner as outlined in Section [5.2.3](#).

Guidelines for management of study treatment in the event that bleeding is observed in patients are provided in [Table 4](#).

#### **5.1.1.4 Cytopenias**

Cytopenias have been observed in patients with hematological malignancies who received GDC-0853, including neutropenia, anemia, and thrombocytopenia; events have been monitorable and clinically manageable (see the GDC-0853 Investigator's Brochure for further details).

Patients should be monitored regularly with hematology laboratory evaluations as outlined in the schedule of assessments and should receive appropriate supportive care as clinically indicated. Patients should be advised to seek immediate medical attention if they develop signs and symptoms suggestive of cytopenias (e.g., persistent fever, bruising, bleeding, pallor).

Guidelines for the management of study treatment, including dose holding, in the event of cytopenias in patients are provided in [Table 4](#).

#### **5.1.1.5 Gastrointestinal Effects**

Body weight gain and food consumption changes have been observed in animals, including nonsignificant increases in male Wistar-Han rats administered  $\geq 2$  mg/kg/day ( $4.3 \mu\text{M}\cdot\text{hr}$ ) for 6 months, and significant reductions in rats administered 100 mg/kg/day ( $1438 \mu\text{M}\cdot\text{hr}$ ) and dogs administered 25 mg/kg ( $180 \mu\text{M}\cdot\text{hr}$ ) for 4 weeks. These effects on body weight gain and food consumption were reversible following discontinuation of GDC-0853 dosing.

Grade 1 diarrhea, nausea, and abdominal pain have been reported in patients with hematological malignancies treated with GDC-0853; however, the events resolved and have not led to study drug discontinuation. Healthy subjects in the multiple ascending-dose study, GA29347, reported events of mild self-limited nausea.

Throughout the study, patients will be monitored for GI side effects. Guidelines for management of study treatment in the event of GI side effects in patients are provided in [Table 4](#).

#### **5.1.1.6 Hepatotoxicity**

Evidence of hepatobiliary injury was observed in animals administered relatively high doses of GDC-0853 in repeat-dose toxicity studies (see Section [1.3.1](#) for related primary nonclinical toxicity findings).

In clinical studies to date, including single dosing and multiple dosing for 14 days in healthy subjects and daily dosing for up to 2 years in patients with hematological malignancies, there have been no adverse events of liver enzyme elevations or trends towards elevations in laboratory evaluations.

As a safety risk-mitigation measure, to be eligible for the study, AST and/or ALT levels should be no more than 1.5 times the ULN and total bilirubin levels should be  $\leq 1.2 \times \text{ULN}$  at screening. Safety monitoring for potential hepatotoxicity includes baseline and routine

evaluations of AST/ALT and total bilirubin levels throughout the study as outlined in the schedule of assessments.

Laboratory results of Grade  $\geq 3$  ( $> 5 \times \text{ULN}$ ) AST or ALT elevation, or ALT or AST elevations  $> 3 \times \text{ULN}$  in combination with clinical jaundice (total bilirubin  $> 2 \times \text{ULN}$ ) are considered AESIs and should be reported to the Sponsor in an expedited manner as outlined in Section 5.2.3.

Guidelines for the management of study treatment in the event of hepatotoxicity in patients are provided in Table 4.

#### 5.1.1.7 Cardiovascular Effects

GDC-0853 is considered to have a low potential to cause QT interval prolongation or to directly affect other cardiovascular parameters, at therapeutic exposures. A minimal increase in corrected QT (QTc; 7 msec or 3%) interval was noted at 45 mg/kg in the single dose cardiovascular safety pharmacology study in telemetry-instrumented dogs. Based on extrapolated/interpolated toxicokinetic data, the unbound  $C_{\text{max}}$  at 45 mg/kg (considered a NOAEL) [REDACTED]

[REDACTED] There were no GDC-0853-related changes in ECG parameters in the repeat-dose 4-week or 9-month dog toxicity studies.

Analysis of ECG data from the SAD and MAD studies in healthy subjects did not demonstrate any significant increase in either QRS interval or QTcF intervals. However, cardiac safety will continue to be evaluated in all patients at baseline and throughout the study, with routine monitoring of vital signs (including heart rate and blood pressure), collection of routine safety ECGs, triplicate ECGs with appropriate PK-matched timepoints, and collection of adverse events (see Appendix 1).

Management of patients with sustained QTcF prolongation (QTcF that is  $> 500$  msec and/or  $> 60$  msec longer than the baseline value on at least two ECG measurements  $> 30$  minutes apart) should include close monitoring, with ECGs repeated at least hourly until two successive ECGs show stabilization of the findings, correction of any electrolyte abnormalities, and possible discontinuation of other concomitant medications that are known to prolong the QT interval. Consultation with a cardiologist or electrophysiologist is recommended, to help in the management of such patients. The Medical Monitor should be notified as soon as possible (see Section 4.5.8.11 and Section 4.5.10)

Guidelines for management of study treatment in the event of cardiovascular effects in patients are provided in Table 4.

#### 5.1.1.8 Vascular Inflammation

[REDACTED]  
[REDACTED]  
[REDACTED] The translatability of the nonclinical findings to

humans is unknown; however, Beagle dogs are susceptible to spontaneous development of polyarteritis syndrome (Snyder et al. 1995) and may be more sensitive to any drug-induced effects. Further, there are several examples of approved therapies for which there is no correlation between the finding of vasculitis in dogs or rats at clinically relevant exposures and adverse outcomes in patients (FDA 2003; FDA 2011).

As a safety risk-mitigation measure, CBC, creatinine, and urinalysis will be monitored in all patients during the study.

Guidelines for management of study treatment in the event of a new treatment emergent vasculitis in patients are provided in Table 4.

#### **5.1.1.9 Malignancy**

The impact of BTK inhibition on the development of malignancies is not known; however, malignancies have been identified as a potential concern for immunomodulatory agents. Malignancies have been reported in patients with XLA, including lymphoreticular malignancies, gastric and colorectal adenocarcinoma, and squamous cell carcinoma of the lung.

Patients with a history of cancer, including hematologic malignancy and solid tumors, within 10 years of screening will be excluded from the study. Basal or squamous cell carcinoma of the skin that has been excised and is considered cured and in situ carcinoma of the cervix treated with apparent success by curative therapy more than 1 year prior to screening are not exclusionary.

All malignancies are considered adverse events of special interest for this study and should be reported to the Sponsor in an expedited manner as outlined in Section 5.2.3.

Guidelines for management of study treatment in the event of malignancies in patients are provided in Table 4. Please refer to the GDC-0853 Investigator's Brochure for further details.

#### **5.1.2 Management of Study Treatment in Patients Who Experience Specific Adverse Events**

Guidelines for management of study treatment in patients who experience specific adverse events are outlined in Table 4.

**Table 4 Guidelines for Management of Study Treatment in Patients Who Experience Specific Adverse Events**

Event	Action to Be Taken a

Infection b
 
Serious infection or any infection requiring treatment with an IV antimicrobial agent
 
Self-limited infections that require treatment
	
Withhold study treatment. Once the infection has resolved, consult with Medical Monitor to discuss potential resumption of study treatment.
 
Withhold study treatment during antimicrobial therapy.

Bleeding
	
Any Grade <math>\geq 2</math> bleeding event is considered an adverse event of special interest and should be reported to the Sponsor in an expedited manner.
 
For Grade 3 or higher bleeding events or any serious bleeding event withhold study treatment and consult with the Medical Monitor. Once bleeding event has resolved, consult with Medical Monitor to discuss the potential resumption of study treatment.

Neutropenia c
 
Grade 2: ANC > 1000 and < 1500/mm^3
 
Grade 3: ANC > 500 and < 1000/mm^3
	
Maintain study treatment dosing.
 
For the first event, hold study treatment and recheck CBC in 7 days. If neutrophil count has recovered to Grade 1 (> 1500/mm^3) or has returned to baseline, study treatment can be resumed unless there is a concurrent serious or Grade 3 infection. If Grade 3 neutropenia persists, or for recurrent Grade 3 neutropenia, discuss with the Medical Monitor.

Grade 4: ANC < 500 /mm^3
	
Discontinue study treatment.

Lymphopenia
 
Treatment emergent Grade 2 lymphopenia: lymphocyte count 500–800/mm^3
 
Treatment emergent Grade 3 lymphopenia: lymphocyte count 200–500/mm^3
 
Grade 4 Lymphopenia: lymphocyte count < 200/mm^3
	
Maintain study treatment dosing unless concurrent active infection or other clinical concern.
 
For the first event, hold study treatment and recheck CBC in 7 days. If lymphocyte count has recovered, study treatment can be resumed unless there is a concurrent serious or Grade 3 infection. If Grade 3 lymphopenia persists, or for recurrent Grade 3 lymphopenia, discuss with the Medical Monitor.
 
Discontinue study treatment.

**Table 4 Guidelines for Management of Study Treatment in Patients Who Experience Specific Adverse Events (cont.)**

Event	Action to Be Taken a

Thrombocytopenia d
 
Treatment-emergent Grade 1: PLT > 75,000/mm^3
 
Treatment-emergent Grade 2: PLT 50,000–75,000/mm^3
 
Treatment-emergent Grade ≥3: PLT < 50,000/mm^3
	
In the absence of bleeding event(s), maintain study treatment dosing.
 
For the first treatment emergent drop in platelet count to 50,000–75,000/mm^3 that cannot be attributed to an SLE flare, hold study treatment and recheck CBC in 7 days. If platelet count has recovered to >75,000/mm^3 or to baseline and there have been no bleeding events, study treatment can be resumed.
 
For recurrent or persistent Grade 2 treatment-emergent thrombocytopenia that cannot be attributed to an SLE flare, or for thrombocytopenia associated with bleeding events, discuss with the Medical Monitor (and consider discontinuing study treatment).
 
For the first treatment emergent drop in platelet count to < 50,000/mm^3 that cannot be attributed to an SLE flare, hold study treatment and recheck CBC in 7 days. If the platelet count has recovered to baseline or >75,000/mm^3, study treatment can be resumed.
 
1) If the platelet count fails to return to baseline or >75,000/mm^3, 2) if there is recurrence of Grade 3 treatment-emergent thrombocytopenia that cannot be attributed to an SLE flare, or 3) if the thrombocytopenia is associated with bleeding events, discuss with the Medical Monitor (and consider discontinuing study treatment).

Grade 4: PLT < 25,000/mm^3
 
Gastrointestinal Effects
 
Nausea, vomiting, and/or diarrhea
 
Malignancy
 
Any malignancy
	
Discontinue study treatment
 
Manage according to site institutional guidelines. Consider administration of GDC-0853 with food as a possible mitigation strategy. Consult with Medical Monitor.
 
Discontinue study treatment with the exception of non-serious local and resectable basal or squamous cell carcinoma of the skin. Report event as an adverse event of special interest to the Sponsor in an expedited manner.

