**Table 4 Guidelines for Management of Study Treatment in Patients Who Experience Specific Adverse Events (cont.)**

Event	Action to Be Taken a
Vascular Inflammation	
Treatment emergent vasculitis	Initiate appropriate evaluation and consult with the Medical Monitor.

ALP=alkaline phosphatase; ALT=alanine aminotransferase; ANC=absolute neutrophil count; AST=aspartate aminotransferase; CBC=complete blood count; ECG=electrocardiogram; IV=intravenous; OLE=open label extension; PLT=platelet count; SLE=systemic lupus erythematosus; ULN=upper limit of normal.

Note: “Study treatment” includes study drug (GDC-0853 or placebo)

- a Patients who discontinue study drug treatment due to an adverse event should remain in the blinded study if feasible however they will not be eligible for an OLE, if initiated. If they discontinue the study, the patient should enter safety follow up.
- b Appropriate laboratory investigations, including but not limited to cultures, should be performed to establish the etiology of any serious infection.
- c Patients withdrawn from the study due to a reduced neutrophil count must be followed closely for signs of infection, with treatment and repeated laboratory analysis as deemed appropriate by the investigator including discontinuation of other treatments if indicated.
- d Patients withdrawn from the study due to a reduced platelet count should have additional management and treatment as deemed appropriate by the investigator including discontinuation of other treatments if indicated.
- e In rare circumstances, it may be acceptable to resume study drug, provided that any ECG abnormalities have resolved and that the patient is appropriately monitored. Prior to re-administering drug, consult with the Medical Monitor. Clinical judgment should be applied.

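### Table 4's platelet hold-and-restart row has no lower limit, so it overlaps and conflicts with the Grade 4 stopping rule below 25,000/mm³

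*Combined protocol and SAP*

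**What the plan says.** Three provisions of the protocol deal with a platelet count below 25,000/mm³.

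- **Table 4 (Section 5.1.2), hold row.** The label is "Treatment-emergent Grade ≥3: PLT" below 50,000/mm³. For the first treatment-emergent drop under 50,000/mm³ that is not attributable to an SLE flare, the action is "hold study treatment and recheck CBC in 7 days. If the platelet count has recovered to baseline or" above 75,000/mm³, dosing may restart. The Medical Monitor is brought in for three situations only: the count does not recover, there is associated bleeding, or "if there is recurrence of Grade 3 treatment-emergent thrombocytopenia that cannot be attributed to an SLE flare".
- **Table 4, Grade 4 row.** Below 25,000/mm³ the action is to discontinue. This row says nothing about restarting.
- **Section 4.6.2.** The list is introduced by "Patients must discontinue study treatment (and will continue in the study) if they experience any of the following" and includes "Grade 4 Thrombocytopenia: platelet count" below 25,000/mm³, with no exception for a first event or a flare. The section closes: "In some cases, study treatment may be resumed if approved by both the investigator and the Medical Monitor".

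Two further texts bear on the point. Section 5.1.1.4 tells sites where to look: "Guidelines for the management of study treatment, including dose holding, in the event of cytopenias in patients are provided in" Table 4. Footnote a to Table 4 says that patients who stop study drug for an adverse event should stay in the blinded study if feasible, "however they will not be eligible for an OLE, if initiated".

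**The concern.** A count of, say, 20,000/mm³ meets the wording of two adjacent rows that prescribe different actions. One is a temporary hold that the site can end after a satisfactory recheck. The other is a discontinuation, which under Section 4.6.2 can be reversed only with two approvals.

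Two things depend on which row is applied. The first is control of the restart: whether the Medical Monitor must agree before a patient who fell below 25,000/mm³ is dosed again. The second is classification. A discontinued patient loses eligibility for the open-label extension under footnote a, and enters the separate Section 6.5 summary of events that led to stopping study drug. A patient who was only held does neither. Sites could therefore treat and report the same event differently.

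**Working it through.** The plan gives no figure to reproduce. The check compares the ranges and then the actions.

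**Inputs.** Hold row: below 50,000/mm³, no lower limit. Grade 4 row and Section 4.6.2: below 25,000/mm³. Entry (Section 4.1.2): a screening count below 50,000/µL is exclusionary (1 µL = 1 mm³). Table 4, neutropenia: Grade 3 is above 500 and below 1,000/mm³, Grade 4 below 500. Table 4, lymphopenia: Grade 3 is 200 to 500/mm³, Grade 4 below 200.

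**Step 1: overlap of the ranges.**
- Platelets: [0, 50,000) ∩ [0, 25,000) = [0, 25,000). This is the whole Grade 4 range.
- Neutrophils: (500, 1,000) ∩ [0, 500) = empty.
- Lymphocytes: [200, 500] ∩ [0, 200) = empty.

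The platelet row lacks the lower limit that the other two cytopenia rows have. The platelet Grade 2 row also has both limits (50,000 to 75,000).

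**Step 2: actions inside the overlap.** These are illustrative cases, each a first drop, not attributed to a flare, without bleeding.

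| Baseline | Lowest count | Day 7 | Hold row | Grade 4 row and 4.6.2 |
|---|---|---|---|---|
| 180,000 | 20,000 | 82,000 | above 75,000: site may restart | discontinue; restart needs both approvals (4.6.2) |
| 52,000 | 20,000 | 52,000 | back to baseline: site may restart | discontinue; restart needs both approvals (4.6.2) |
| 180,000 | 20,000 | 60,000 | not recovered: discuss with Medical Monitor | discontinue; restart needs both approvals (4.6.2) |

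The second case is possible because entry requires only 50,000 and recovery to baseline is enough. The third shows that the hold row gives no unsupervised restart when recovery is incomplete.

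**Step 3: when the hold row omits the Medical Monitor.** All four conditions must hold: first drop, not attributable to a flare, recovered at recheck, no bleeding. If the drop is due to a flare, the hold action does not apply. If it recurs, fails to recover or comes with bleeding, the same cell sends the case to the Medical Monitor.

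**Step 4: depth of the fall.** With screening at 50,000 or more, a count below 25,000 is a fall of more than 1 − 25,000/50,000 = 50% from the screening value.

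**Step 5: after the correction.** [25,000, 50,000) ∩ [0, 25,000) = empty, and the two rows together still cover [0, 50,000) without a gap.

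**The case against.** The strongest reply is that the protocol, read as a whole, already gives the answer. The hold row is permissive and Section 4.6.2 is mandatory, so a site that discontinues complies with both, while a site that restarts alone breaches 4.6.2. Letting the hold row control below 25,000/mm³ would empty the Grade 4 row of effect for a first, recovered, non-flare event. The later wording in the same cell, "if there is recurrence of Grade 3 treatment-emergent thrombocytopenia that cannot be attributed to an SLE flare", suggests that the row was meant for Grade 3 alone. Nesting with the more severe entry controlling also occurs elsewhere in Table 4, in the bleeding and liver entries. And a restart would not go unseen: a laboratory result that interrupts treatment must be reported as an adverse event (5.3.5.4), hematology goes to a central laboratory whose data reach the sponsor directly (4.5.9, 7.1), and the Internal Monitoring Committee reviews safety throughout (3.1.2, 5.1).

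Most of this stands. Section 4.6.2 is the likelier intended rule. It does not remove the conflict. No text ranks Table 4 against 4.6.2 or one row against another, and the table to which 5.1.1.4 sends sites contains both instructions. The other nested entries are less of a problem: the bleeding actions add to each other, and the milder liver row already requires Medical Monitor consultation. The safeguards make the event visible, but none of them is an approval before restart.

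**Conclusion.** The point holds as an internal inconsistency in a safety rule. The hold row's range contains the entire Grade 4 range and attaches a different action to it. The conclusion rests on the wording alone and needs no outside figure.

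Its size is small. It concerns one approval step and the classification of the event, and only under the four conditions listed above. Both texts stop dosing at once and both leave some route to resumption. The documents give no frequency for such events, and none is assumed. Power and the primary analysis are untouched: efficacy is analysed by intention to treat, and patients who stop treatment are asked to complete their visits.

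A reader might infer that the protocol lets a site restart on recovery alone after a count below 25,000/mm³. The documents do not support that: one row, read in isolation, says so, against a mandatory list in 4.6.2. A reader might also infer that the Grade 4 row itself demands two approvals; that requirement is in 4.6.2 only. Nor does the hold row leave out the Medical Monitor when there is bleeding.

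One detail stays open: footnote a does not say whether a patient who is discontinued and later resumed under 4.6.2 regains eligibility for the extension.

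**What to change.** In Table 4, relabel the row *Treatment-emergent Grade 3: PLT 25,000 to < 50,000/mm³* and put the same range in its action text, where the open limit is repeated. Leave the Grade 4 row as it is, in line with Section 4.6.2, so that any restart after a count below 25,000/mm³ goes through the approval by investigator and Medical Monitor set out there.

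The cost is one row label and one range in the next amendment. Data collection and analysis do not change.
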